#### 7.5.4 Observational endpoints

- 1. Admission rates, for
  - (a) Influenza,
  - (b) RSV, and
  - (c) S. pneumoniae

#### 7.6 Statistical analysis

All analyses for both process and clinical outcomes will be based on Intention to Treat (ITT) analyses.

Impact of test result on prescribing The time to prescription of `narrow spectrum', `oral antibiotics' or `no antibiotics' between the three groups will be assessed using survival analysis techniques, whilst the use of neuraminidase inhibitors in those with influenza will be assessed using  $\chi^2$  tests, together with 95% CIs. Further analyses to allow for potential differences in patient demographics and baseline clinical characteristics between the three diagnostic test groups, and not allowed by stratification, will make use of cox proportional hazards regression modelling in the case of time to appropriate prescribing and logistic regression techniques in the case of neuraminidase inhibitors.

*Length of hospital stay* Length of hospital stay in the three diagnostic groups will initially be compared using non-parametric methods. Further analyses to allow for potential differences in patient demographics and baseline clinical characteristics between the three diagnostic test groups, and not allowed by stratification, will make use of generalised linear models in order to accommodate any skewness in the data.

*Mortality rates* Mortality rates between the three diagnostic testing groups will be compared by means of a Log-Rank Test and Kaplan-Meier survival curves. Adjustment for potential differences in patient demographics and baseline clinical characteristics between the three diagnostic test groups, and not allowed by stratification, will make use of Cox proportional hazards regression methods.

*Diagnostic accuracy* Sensitivity, specificity, positive predictive value of molecular and near patient diagnostic tests in comparison to traditional laboratory methods will be calculated together with 95% CIs. Heterogeneity in the sensitivity and specificity with respect to patient demographics and baseline clinical characteristics will be explored as secondary analyses using patient defined sub-groups.

Admission to intensive care The proportions of patients in the three groups who are admitted to intensive care within the first 10 days of admission will be compared using  $\chi^2$  tests, together with 95% CIs. Further analyses to allow for potential differences in patient demographics and baseline clinical characteristics between the three diagnostic test groups, and not allowed by stratification, will make use of logistic regression techniques.

*Ventilatory support* The proportions of patients in the three groups who receive ventilatory support within the first 10 days of admission will be compared using  $\chi^2$  tests, together with 95% CIs. Further analyses to allow for potential differences in patient demographics and baseline clinical characteristics between the three diagnostic test groups, and not allowed by stratification, will make use of logistic regression techniques.

Appropriate use of isolation facilities In patients with confirmed influenza or RSV the time taken from admission to the MAU to admission to a single room (isolation cubicle) will be compared between the three diagnostic groups by means of a Log-Rank Test and Kaplan-Meier survival curves. Adjustment for potential differences in patient demographics and baseline clinical characteristics between the three diagnostic test groups, and not allowed by stratification, will make use of Cox proportional hazards regression methods.

*Quality of Life (EQ-5D)* Quality of life in the three diagnostic groups will initially be compared using non-parametric methods. Further analyses to allow for potential differences in patient demographics and baseline clinical characteristics between the three diagnostic test groups, and not allowed by stratification, will make use of generalised linear models in order to accommodate any skewness in the data.

*Speed of Tests* Time taken to receive test results in the three diagnostic groups will initially be compared using non-parametric methods. Further analyses to allow for potential differences in patient demographics and baseline clinical characteristics between the three diagnostic test groups, and not allowed by stratification, will make use of generalised linear models in order to accommodate any skewness in the data.

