#### **1.6** Diagnostic tests for influenza

Viral isolation and haemagglutination inhibition antibody testing are standard methods for influenza diagnosis, but have drawbacks. Virus isolation by culture from respiratory secretions may take a week or

more (a median of 8 days in one recent study); it requires specialised laboratory facilities; and does not provide results that could influence the initiation of treatment. Serology provides a retrospective diagnosis. Neither test alone is considered a 'gold standard' for influenza diagnosis, since each lacks sensitivity, but culture and serology together have been used as 'gold standard' to assess molecular diagnosis.

Tests for rapid diagnosis of influenza A and B virus by immunofluorescence of exfoliated nasopharyngeal cells have shown variable sensitivity (40 to 100%) and specificity (86 to 99%); they require specialist equipment and expertise and are labour intensive. Rapid, near-patient tests for influenza vary in complexity, sensitivity, and specificity. They can aid clinical management, but their value in the hospital setting in influencing prescribing and infection control is unclear. We plan to use the Quidel QuickVue influenza A and B test. It is the most rapid of the near patient tests; is particularly simple to perform; and has a median sensitivity and specificity of 80%. Its diagnostic accuracy in the elderly is unknown. Molecular diagnosis of influenza by reverse transcription PCR (RT-PCR) provides improved sensitivity and specificity, allows accurate detection, and facilitates the subtyping of influenza. Multiplex PCR has the added advantage of allowing identification of several infectious agents (e.g., influenza subtypes A/H1N1, A/H3N2, and B, and RSV types A and B) in one sample and in one reaction. The technique is used routinely within the specialist diagnostic facilities of the Health Protection Agency, Colindale, where it has a sensitivity of 92% and specificity of 84%. We plan to evaluate the ease of use and usefulness of PCR in Leicester as part of the process of distributing it more widely.

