#### **2 OBJECTIVES OF THE STUDY**

#### 2.1 Research objectives and hypotheses

In the Medical Admissions Units/Wards of the University Hospitals of Leicester, to:

1. Determine the diagnostic accuracy (sensitivity, specificity, positive and negative predictive values) of rapid molecular and near patient diagnostic tests for influenza, RSV and *S. pneumoniae* infections in comparison to traditional laboratory culture.

The increased diagnostic accuracy of rapid molecular and near patient tests over traditional laboratory methods improves patient management through better use of antimicrobials and isolation facilities. Rapid molecular and near patient diagnostic tests for influenza, RSV and S. pneumoniae infections are more cost-effective than traditional laboratory diagnostic tests.

2. Assess the potential benefits of ease of use, and speed of rapid molecular and near patient diagnostic tests for influenza, RSV and *S. pneumoniae* infections, in comparison to traditional laboratory culture.

Rapid molecular and near patient diagnostic tests for influenza, RSV and S. pneumoniae infections provide benefits in terms of (a) ease of use, and (b) more rapid results, in comparison to traditional laboratory culture.

3. Determine whether rapid molecular and near patient diagnostic tests for influenza, RSV and *S. pneumoniae* infections have any impact on prescribing.

Rapid molecular and near patient diagnostic tests for influenza, RSV and S. pneumoniae infections result in earlier use of narrow-spectrum antimicrobial therapy; and/or an earlier switch from intravenous to oral therapy; and/or earlier discontinuation of antibiotics in patients infected with influenza and RSV - in comparison to traditional laboratory culture

4. Determine whether rapid molecular and near patient diagnostic tests for influenza, RSV and *S. pneumoniae* infections allow more appropriate use of isolation facilities, in comparison to traditional laboratory culture.

Rapid detection of influenza and RSV by rapid molecular and near patient diagnostic tests leads to the appropriate isolation of patients, but only in hospitals/wards with an adequate provision of cubicles.

5. Compare the costs of performing rapid molecular and near patient diagnostic tests for influenza, RSV and *S. pneumoniae* infections, in comparison to traditional laboratory culture.

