- Based on the above, we expect to recruit 747 participants with pneumonia, of whom at least one third (n=249) should have *S. pneumoniae* infection. Of these, ~83 should be randomly allocated to the rapid near patient test (Binax NOW); the remainder will be randomised to the group tested by traditional methods. Thus the speed of diagnosis, impact of early diagnosis on prescribing, clinical outcomes, and costs will be assessed in groups having an estimated 83 and 166 subjects. However, as identical sample sets will be taken from each participant, the diagnostic accuracy of the tests will be assessed in all 249 subjects. The number of cases of *S. pneumonaie* infection that are likely to be identified among the anticipated 649 (556 +93) participants with unspecified acute lower respiratory tract infections is unknown, but their occurrence will add to the pool of cases for studies of diagnostic accuracy.
- On the basis of the Rochester study, we expect that 10% of the 2752 elderly (≥65 years) participants will have influenza A or B. Of the 275, one third (~92) will be allocated to the QuickView near patient influenza immunoassay; one third will be allocated to the rapid molecular group; the remainder will be allocated to the group tested by traditional methods. Identical sample sets will be taken from each individual, so the diagnostic accuracy of the tests will be assessed in all 275 subjects.
- Similarly, we expect that 5% of the 2752 elderly (≥65 years) participants will have RSV A or B. Of the 138, one third (~46) will be allocated to the rapid molecular group; the remainder (~92) will be allocated to the group tested by traditional methods. We expect that very few of these will be found

positive by the routine tests employed. Identical sample sets will be taken from each individual, so the diagnostic accuracy of the tests will be assessed in all 138 subjects.

While the numbers of patients with influenza and RSV who are allocated to the 'rapid' near patient or molecular tests are comparatively small (~92 + ~46 per elderly group, plus cases occurring in the 18-64-year-olds), the impact of a 'viral' infection (RSV or influenza) infection on patient isolation, antimicrobial prescribing, and clinical outcomes may be compared using a larger combined group – i.e.,

Elderly

Rapid influenza & RSV (i.e., Quickview + molecular tests) n=(92+92+46)=230Traditional influenza & RSV n=(92+46+46)=184

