#### 7.3 Definitions of influenza, RSV and S. pneumoniae positivity

Influenza positive Patients will be considered influenza positive if:

- The Quidel QuickVue Influenza A and B test is positive, and/or
- The multiplex PCR is positive, and/or
- Viral culture is positive, and/or
- Serology results indicate influenza infection (e.g., 4-fold increase in influenza A H3N2, H1N1, or influenza B HI antibody from acute to convalescent sera).

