#### 7.5.3 Endpoints for laboratory assessment of diagnostic tests

- 1. Diagnostic accuracy,
  - (a) Sensitivity,

- (b) Specificity
- (c) Positive predictive value,
- (d) Negative predictive value, and
- (e) Discrepant analysis of near patient and molecular diagnostic tests,

will be estimated in comparison with traditional and other (e.g., serology) laboratory tests.

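### The reference standard for diagnostic accuracy differs between sections; if culture alone is used, as Objective 1 says, specificity and PPV are biased downward and no test can be shown to be more accurate than culture

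*Protocol*

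**What the plan says.** Three sections describe the comparator for accuracy, and they differ.

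- Section 2.1, Objective 1: accuracy of the rapid tests for the three "infections in comparison to traditional laboratory culture".
- Section 7.6: "Sensitivity, specificity, positive predictive value of molecular and near patient diagnostic tests in comparison to traditional laboratory methods", with 95% confidence intervals.
- Section 7.5.3: sensitivity, specificity and predictive values "will be estimated in comparison with traditional and other (e.g., serology) laboratory tests". The same list includes "Discrepant analysis of near patient and molecular diagnostic tests". The synopsis has matching wording.

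The hypothesis under Objective 1 starts from superiority over the comparator: "The increased diagnostic accuracy of rapid molecular and near patient tests over traditional laboratory methods improves patient management".

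The background sections describe that comparator as weak. On culture and serology for influenza, section 1.6 says: "Neither test alone is considered a 'gold standard' for influenza diagnosis, since each lacks sensitivity"; it adds that the two together have served as a gold standard. Section 1.7 calls virus culture insensitive for RSV in the elderly. Section 1.8 says that no highly sensitive and specific reference exists for pneumococcal pneumonia, that blood culture is positive in under 10% of community-acquired pneumonia, that sputum yield is under 25%, and that antibody measurement is unreliable.

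Section 7.3 separately defines a positive patient by any positive test. For influenza its list begins "The Quidel QuickVue Influenza A and B test is positive, and/or".

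Section 7.1 assesses accuracy in all 138 expected elderly RSV cases. Of the roughly 92 in the traditionally tested groups it says: "We expect that very few of these will be found" positive by the routine tests.

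**The concern.** A test compared with culture as the sole reference can at best equal culture, because culture then has 100% sensitivity and specificity by definition. A premise that the rapid tests are more accurate than culture cannot be examined on those terms.

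The estimates also become biased. Each true infection that culture misses and the rapid test finds is entered as a false positive, which lowers specificity and, much more, PPV. The protocol expects such cases: section 1.2 expects molecular tests to identify more RSV, and the synopsis expects the antigen test to identify more pneumococcal disease than the historical estimate.

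Section 1.11 calls technology assessment the primary driver of the study, and cost per case detected depends on who counts as a case. An unsettled reference therefore affects central results.

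**Working it through.** **The plan's own figure.** Section 7.4 gives precision as 2SE. With 2SE = 2√[p(1−p)/(N × 0.8 × prevalence)], N = 2752 and p = 0.80:

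- 10% prevalence: 220 cases, 2√(0.16/220.16) = 5.4%
- 5% prevalence: 110 cases, 2√(0.16/110.08) = 7.6%

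These are the protocol's numbers with the two prevalence labels exchanged. That is a separate error. What matters here is that the denominator is every truly infected patient, not every culture-positive patient.

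**Specificity and PPV against culture alone.** Take 1000 patients, 100 infected (10% influenza prevalence, section 7.1). Assume culture has sensitivity c, specificity 100%, and errors independent of PCR given true status. The protocol gives no value for c, so 80, 60 and 40% are assumed.

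- Culture-negative patients = 100(1−c) + 900
- PCR positives among them = 100(1−c) × 0.92 + 900 × (1 − Sp)
- Apparent specificity = 1 − (second ÷ first)
- Apparent PPV = 100c × 0.92 ÷ all PCR positives

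Case A uses PCR at 92% sensitivity and 84% specificity, both from section 1.6. There are 92 + 144 = 236 PCR positives, so true PPV is 92/236 = 39%.

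| c | Apparent specificity | Apparent PPV |
|---|---|---|
| 80% | 1 − 162.4/920 = 82.3% | 73.6/236 = 31% |
| 60% | 1 − 180.8/940 = 80.8% | 55.2/236 = 23% |
| 40% | 1 − 199.2/960 = 79.3% | 36.8/236 = 16% |

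Case B keeps 92% sensitivity and assumes 99% true specificity, because the 84% may itself reflect an imperfect reference. There are 92 + 9 = 101 PCR positives, so true PPV is 91%.

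| c | Apparent specificity | Apparent PPV |
|---|---|---|
| 80% | 1 − 27.4/920 = 97.0% | 73.6/101 = 73% |
| 60% | 1 − 45.8/940 = 95.1% | 55.2/101 = 55% |
| 40% | 1 − 64.2/960 = 93.3% | 36.8/101 = 36% |

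**Pneumococcus.** Section 7.1 takes one third of pneumonia as pneumococcal. If under 10% of pneumonia patients have a positive blood culture of any kind, blood culture alone finds under 0.10/0.333 = 30% of them (this combines figures from different sources, so it is only a guide). Per 300 pneumonia patients with 100 infected, a perfect test judged against a reference of 30% sensitivity would show specificity 200/(200 + 70) = 74.1% and PPV 30%. Adding sputum culture raises the reference sensitivity; at 70% the figures are 200/230 = 87.0% and 70%. Serology cannot help for this pathogen.

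**RSV denominators.** After the 20% dropout, 110 RSV cases are expected. If culture finds 80, 60, 40 or 20% of them (assumed), there are 88, 66, 44 or 22 reference-positive patients, and 2SE at 80% sensitivity is 8.5, 9.8, 12.1 or 17.1 points instead of 7.6. The remark in section 7.1 about routine tests points to the lower end but gives no yield.

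**Discrepant resolution, if it were used to revise estimates.** Suppose only QuickVue-positive, culture-negative samples are retested. With QuickVue sensitivity 80% (section 1.6), culture 50% and a retest of 90% sensitivity (both assumed) and perfect specificity, 100 infected give 50 culture-positive (40 found by QuickVue) and 40 discordant, of which 36 are confirmed. Apparent sensitivity is (40 + 36)/(50 + 36) = 88.4%, against a true 80%.

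**The case against.** The best defence is that the plan is not confined to culture. The synopsis and section 7.5.3 name serology as a comparator, section 6.2.12 collects paired sera for influenza and RSV, and section 9 schedules the serology. Section 1.6 counts antibody testing among the standard methods for influenza, so the traditional methods of section 7.6 could include it. This stands. A reader might infer that superiority over culture can never be shown in this trial; that follows only if culture is the sole reference. With serology as reference, the sensitivities of PCR, QuickVue and culture can all be estimated.

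Two other strong readings also go beyond the text. One is that discrepant analysis will inflate the estimates: section 7.5.3 lists it beside sensitivity and specificity and does not say that it revises them. The other is that the any-positive definition in section 7.3 is the accuracy reference: it is written for defining case populations. If it were used that way it would include the index tests and make their specificity 100% automatically, but the protocol does not say so.

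It can also be said that the first hypothesis concerns patient management, which the randomised comparison tests, and that accuracy is only its premise. That is fair, but Objective 1 is to determine accuracy.

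The defence does not remove the conflict. Objective 1 says culture, the endpoint section says more than culture, and the analysis section can be read either way. Nor does serology rescue the pneumococcal estimates.

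**Conclusion.** The concern holds in a limited form. The accuracy reference is stated inconsistently, and the reading fixed by Objective 1 produces a known bias against the rapid tests. On that reading the accuracy premise of the first hypothesis cannot be tested.

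Over the assumed range of culture sensitivity, PCR specificity falls by about 2 to 5 points at the protocol's 92/84 and by 2 to 6 points at 92/99. PPV falls from 39% to between 31 and 16%, or from 91% to between 73 and 36%. The problem is greatest for pneumococcus, where the protocol itself says that no good reference exists. The stated precision rests on all infected patients, more than a culture reference will find.

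These sizes rest on assumed culture sensitivity, perfect culture specificity and independent errors. If culture and the rapid test tend to miss the same patients, the loss of specificity is smaller and sensitivity is overstated. The documents do not support the claim that the whole accuracy analysis is tied to culture.

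**What to change.** In sections 2.1, 7.5.3 and 7.6, state one reference per pathogen that excludes the test being evaluated and is applied to all patients with the needed samples.

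- Influenza and RSV: culture and/or a 4-fold or greater rise in paired sera. Report culture's own sensitivity too, for example against serology, so that it can be compared with PCR and QuickVue on equal terms.
- S. pneumoniae: report against culture, and label specificity and PPV as lower bounds (this takes culture positives as true infections; section 1.8 warns that sputum growth may be colonisation).
- State that the any-positive definition in section 7.3 is not the accuracy reference, and that discrepant resolution does not revise sensitivity or specificity. Show the discordant cells descriptively.
- Restate precision for the expected number of reference-positive patients.
- A latent-class analysis is optional.

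The cost is wording and a few tables, with no new samples. The downsides are that bias is reduced but not removed, that patients without convalescent serum (taken from survivors at 10 to 90 days) have an incomplete reference, and that the stated precision becomes less favourable.

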#### 2. Length of Stay

2752 patients would enable a Minimum Clinically Significant Difference (MCSD) [between diagnostic policies] of 1 day in the mean length of stay (assuming SD=6 days) to be detected at the 5% significance level with over 80% power, assuming a 20% dropout rate and adjusting for the fact that there are 3 groups.

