#### 3. Appropriate Isolation Levels:

2752 patients would also enable a Minimum Clinically Significant Difference (MCSD) [between diagnostic policies] of an improvement in appropriate use of isolation facilities from 5% to 15% to be detected at the 1% significance level with over 95% power, assuming a 20% dropout rate and adjusting for the fact that there are 3 groups.

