  First, the proportion of patients with *S. pneumoniae* infection in Groups 1, 2, and 3.
  Second, to better define the burden of influenza and RSV, the proportion of all patients with (i) influenza, and (ii) RSV, who die.
- 3. Quality of life, as measured by EuroQol, and quality adjusted life years generated during the 28 days after admission, will be assessed:
  - (a) In all patients in Groups 1, and 2 in comparison to Group 3.

- (b) Second, in patients in patients with (i) influenza, (ii) RSV, and (iii) *S. pneumoniae* in Groups 1, and 2, in comparison to Group 3.
- 4. Use of isolation facilities
  - (a) The time from admission to the MAU to the time of admission to a single room (isolation cubicle) will be compared for patients with confirmed influenza or RSV in Groups 1, 2, and 3.
  - (b) The proportion of patients with influenza or RSV in Groups 1, 2, and 3 who are isolated at any stage during the first 120 hours of the admission.
  - (c) The proportion of patients with *S. pneumoniae* infection in Groups 1, 2, and 3 who are inappropriately isolated for >12 hours.

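### Kaplan-Meier curves for time to a single room ignore discharge and death as competing events and, under ordinary censoring, overstate the share isolated by an amount the protocol does not let one pin down

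*Protocol*

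**What the plan says.** Section 7.5.1, item 4, has two endpoints on isolation in patients with influenza or RSV. Under 4(a), "The time from admission to the MAU to the time of admission to a single room (isolation cubicle) will be compared" across the three groups. Under 4(b), the endpoint is the proportion "who are isolated at any stage during the first 120 hours of the admission".

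Section 7.6 fixes the method for 4(a): "In patients with confirmed influenza or RSV the time taken from admission to the MAU to admission to a single room" "will be compared between the three diagnostic groups by means of a Log-Rank Test and Kaplan-Meier survival curves", with Cox regression for adjustment. The synopsis has the same text. Neither place says what happens to a patient who leaves hospital or dies without having been isolated. Section 7.6 discusses patients not discharged by 28 days and the resulting censoring, but only for costs.

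Three other facts bear on the point:
- Isolation status is followed for the first 7 days only (sections 4.1 and 6.2.3).
- Duration of stay until discharge or death, and deaths to 28 days, are already collected (sections 4.1, 6.2.10 and 6.2.11).
- Earlier discharge with rapid testing is part of a study hypothesis (section 2.1, item 8), and section 7.4 powers a difference between policies of "1 day in the mean length of stay (assuming SD=6 days").

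**The concern.** Kaplan-Meier estimates the share of patients with an event on the footing that a censored patient could still have it later. Discharge and death do not fit: they end any chance of a single room in that admission. With those patients censored, the curve describes a hypothetical ward that nobody leaves, and it sits above the share actually isolated.

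Two things are at stake. First, a reader of the published curve will take its height at 120 hours as the share isolated, and that height can differ from the 4(b) proportion in the same patients. Second, stays may be shorter in the rapid-test groups. Two groups could then show identical curves while different shares were actually isolated.

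**Working it through.** **Inputs from the protocol.** Section 7.1 expects "92 + ~46 per elderly group, plus cases occurring in the 18-64-year-olds", so 92 + 46 = 138 elderly patients per group (2752 × 10% / 3 = 91.7; 2752 × 5% / 3 = 45.9). The isolation rates of 5% and 15% come from section 7.4, item 3, the SD of stay of 6 days from section 7.4, item 2, and the horizons of 120 hours and 7 days from sections 7.5.1 and 6.2.3.

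**The plan's own figure.** Section 7.4 gives the target as "improvement in appropriate use of isolation facilities from 5% to 15% to be detected at the 1% significance level with over 95% power". The same sentence allows for 20% dropout and for having three groups. With 2752 / 3 × 0.8 = 734 per group, a two-sided comparison of 5% with 15% has 99.98% to 99.99% power at significance levels from 0.01/3 to 0.01, so the statement is reproduced. It concerns a proportion and counts all randomised elderly patients. The rates are borrowed here only to set a scale for 4(a).

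**Assumptions not in the protocol.** Mean stay 6, 8 or 10 days, lognormal. The isolation hazard is either constant or decays as exp(−t/τ). With τ = 1 day, 1 − exp(−1) = 63% of the cumulative hazard falls in the first day. With τ = 0.5 day it is 1 − exp(−2) = 86%. Under these stays, 58%, 36% and 17% of patients have left by day 5, and 73%, 55% and 36% by day 7.

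**Formulas.** With isolation hazard h(t), cumulative hazard H(t), and S(t) the probability of still being in hospital:
- true share isolated: F(t) = ∫₀ᵗ h(u) exp(−H(u)) S(u) du
- one minus Kaplan-Meier, with discharge and death censored: 1 − exp(−H(t)) = ∫₀ᵗ h(u) exp(−H(u)) du

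Because S(u) ≤ 1, the second is never below the first. The hazard is set so that F(120 h) is 15% or 5%. The yardstick is SE = √(p(1 − p)/138). At 15% this is √(0.15 × 0.85/138) = 3.04 points.

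**Constant hazard, 15% isolated by 120 h**

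| Mean stay | 120 h: true / 1−KM | Excess | 7 days: true / 1−KM | Excess |
|---|---|---|---|---|
| 6 days | 15.0 / 20.0% | 5.0 points, 1.65 SE | 17.3 / 26.8% | 9.5 points, 2.95 SE |
| 8 days | 15.0 / 16.9% | 1.9 points, 0.61 SE | 18.2 / 22.8% | 4.6 points, 1.39 SE |
| 10 days | 15.0 / 15.6% | 0.6 points, 0.19 SE | 19.1 / 21.1% | 2.0 points, 0.60 SE |

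Check of the first row: 20.0% at 5 days means h = −ln(0.80)/5 = 0.0446 per day, and at 7 days 1 − exp(−7 × 0.0446) = 26.8%.

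**Constant hazard, 5% isolated by 120 h.** The excess at 120 h is 0.94, 0.35 and 0.11 SE for mean stays of 6, 8 and 10 days. At 7 days it is 3.4, 1.6 and 0.7 points (1.7, 0.8 and 0.35 SE).

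**Early isolation.** With τ = 1 day, every combination of these stays and rates gives 0.01 to 0.35 SE at both horizons. With τ = 0.5 day, every one is below 0.1 SE.

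**Shape of the stay distribution.** An exponential stay with mean 6 days also has SD 6. At 120 h a true 15% then reads 21.7% (constant hazard), 17.3% (τ = 1 day) or 16.2% (τ = 0.5 day). That is 1.5, 0.66 and 0.36 of the Kaplan-Meier estimate's own, larger SE; on the binomial yardstick the first is 6.7/3.04 = 2.2.

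**Unequal stays.** Take two arms with the same constant isolation hazard and mean stays of 7 and 6 days. The true shares at 120 h are 15.0% and 13.5%, while both curves read 18.1%. The hidden difference is 1.5 points against an SE of the difference of √(0.15 × 0.85/138 + 0.135 × 0.865/138) = 4.2 points, or about 0.36 SE.

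**The case against.** The strongest reply has four parts.

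*The censoring rule is not stated and may sit in the SAP.* This is true. If patients who leave unisolated are kept at risk to the horizon, one minus Kaplan-Meier equals the crude share and the bias vanishes. But the protocol itself names the curves as the method, and ordinary use of that method censors at discharge and death. What stands is that the bias is conditional on that usage.

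*The share isolated already has its own endpoint.* This also stands. Endpoint 4(b) is free of this bias, and nowhere does the protocol say that one minus Kaplan-Meier will be reported as the proportion. Endpoints 4(a) and 4(b) address speed and share, so different answers are not in themselves a contradiction.

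*The planned test is sound.* With discharge and death censored, the log-rank test compares cause-specific hazards of entering a room. A reader might infer that the group comparison is invalid; it is not. Nor is the stated power undermined, since it concerns a proportion and not 4(a).

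*The size depends on chosen inputs.* A reader might infer that the bias exceeds half a standard error in most plausible settings. The documents do not support that. Over a wider grid of 1,560 settings (mean stay 4 to 12 days, several stay distributions and isolation timings, 110 to 156 per group, 5% to 50% isolated), it does so in 40%, or 44% with the binomial SE. At 5% to 15% isolated the figures are 31% and 35%. It is a majority mainly when isolation is spread evenly over the week.

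The protocol points both ways on timing. Near-patient results are delivered on Day 1 (synopsis, baseline procedures), and some patients may already be in a single room when specimens are taken (section 6.1.15). Yet viral culture may take a week or more (section 1.6), and more cases are expected than can be isolated (section 2.2), so some may wait.

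**Conclusion.** The point holds, in limited form. Section 7.6 specifies Kaplan-Meier curves for an event that discharge and death preclude, and names no competing event. Under ordinary censoring the direction of the error is certain: the curves can only overstate the share isolated. Its size is not known. For lognormal stays with mean 6 to 10 days and SD 6, 5% to 15% isolated and 138 per group, it lies between about zero and about 1.7 SE at 120 hours, and up to about 3 SE at 7 days. The upper ends need both a short stay and isolation spread evenly over the week. The fault is in reading the curves as shares, not in the hypothesis test.

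**What to change.** In section 7.6 and the matching synopsis text, replace the Kaplan-Meier curves for 4(a) with the cumulative incidence of entry to a single room, with discharge alive and death as competing events. Report it with 95% CIs at 120 hours. With every patient's status known to that time it equals the 4(b) proportion, so the two endpoints agree. Keep the log-rank test and the Cox model, and label both as comparisons of cause-specific hazards. Gray's test is not required: it also responds to differences in discharge, which is a separate question.

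The cost is small. Discharge and death are already recorded, and no change to design, sample size or patient care follows. The downside is a little more analysis work and a slightly lower plotted share isolated.
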